1 PROTOCOL SUMMARY

1.1 SYNOPSIS

Title:	Visual rehabilitation in a pediatric population of patients with homonymous hemianopia: a pilot study on virtual-reality stimulation.
Study Description:	Pilot, Open label, Non-randomized study to assess the feasibility of home-based audiovisual immersive virtual-reality stimulation in pediatric patients with homonymous hemianopia.
Objectives:	Primary Objective: Feasibility Secondary Objective: Visual acuity, reading speed, field of vision, quality of life.
Endpoints:	Primary Endpoint: Completion of the home-based audiovisual virtual-reality stimulation procedure (15 sessions).
Study Population:	Male and female patients > 8 years-old with diagnosed homonymous hemianopsia with no prior visual rehabilitation interventions. A total of 10 patients (5 with chiasmatic lesions and 5 with lesions outside of the optic chiasma)
Phase:	Pilot Study
Description of Study Intervention:	Home-based audiovisual immersive virtual-reality stimulation (15 minutes every 2 day for 4 weeks)
Study Duration:	2 years
Participant Duration:	7 months

1.2 SCHEMA

1.3 SCHEDULE OF ACTIVITIES (SOA)

	Inclusion	Baseline	Treatment																Follow-up	
Day	0	0	1	3	5	7	9	11	13	14	15	17	19	21	23	25	27	28	58	200
Visit #		1								2								3	4	5
Fixation stability		X								X								X	X	X
BCVA		X								X								X	X	X
Contrast sensitivity		X								X								X	X	X
MNREAD test		X								X								X	X	X
CVFQ		X								X								X	X	X
Humphrey Full Field 120		X																X	X	X
Esterman binocular		X																X	X	X
VRIFE	X		X	X	X	X	X	X	X	X	X	X	X	X	X	X	X			
IVR	X		X	X	X	X	X	X	X	X	X	X	X	X	X	X	X			

2 INTRODUCTION

2.1 STUDY RATIONALE

Central nervous system tumors are the second most common malignancies in childhood¹. A brain tumor and its treatment can affect the visual system at different levels, from the optic nerves (through compression or infiltration), to sub-cortical structures such as the superior colliculus (SC) and lateral geniculate nuclei (LGN) to optic tracts, optic radiations and visual cortices^{1,2}. Children with brain tumors can present visual impairments like decreased visual acuity and contrast sensitivity, loss of color vision, and visual field loss such as hemianopias¹⁻³. Hemianopia patients present difficulties in detecting stimuli in the defective visual field and show defective scanning and exploration⁴. Moreover, they show a rotation and compression of the auditory space leading to imprecise localization of sound across both hemispaces⁵. Hemianopia patients naturally develop oculo-motor strategies to compensate for visual field loss, but visual rehabilitation procedure must still be developed to optimize/improve visual perception in the blind field. Several studies demonstrated that hemianopia patients could improve visual perception in the damaged hemifield after a stimulation procedure where auditory and visual stimuli were temporally and spatially correlated^{6,7}. Such

audiovisual stimulation programs induce a functional and anatomical reorganization of the visual connectivity in sub-cortical and cortical structures over time⁸⁻¹⁰.

The current strategies rely on a significant workload, over 30 hours of audiovisual stimulation using static, spatially and temporally coherent stimuli displayed on large screens/panels in a clinical setting. These strategies require frequent visits to the clinic impeding the patients' adherence and compliance and increasing the burden of disease. We seek to develop an audiovisual stimulation procedure using immersive virtual-reality (IVR) in head-mounted display (HMD). This is an emerging and very promising visual rehabilitation approach using high-technology devices¹¹⁻¹⁵. It is developed to provide sensory stimulation with better ecological validity due to virtual-reality, greater flexibility due to home-based programs and improved efficiency due to patient-tailored protocols^{11,12}. IVR is a versatile technology, allowing its potential use for the rehabilitation of a variety of low-vision conditions. There are currently limited practical results whether this technology is suitable for low-vision patients to use at home and if it can be deployed on a large scale. A few case report/series studies suggested a potential effectiveness of IVR on visual perception in teenagers, adults and elderly^{12,14,16} but more information as to the potential of use and effectiveness of this technology in children and young teenagers is necessary.

2.2 BACKGROUND

Evidence in the literature¹¹⁻¹⁶ support the hypothesis that an IVR audiovisual stimulation approach using the binocular 3D multiple object tracking (3D-MOT) in the head-mounted display (HMD) Oculus Go/Quest could provide a suitable visual rehabilitation approach for children with visual field defects. The central features of the 3D-MOT closely match attentionally demanding real-life situations^{17,18}. The setup of the task is highly dynamic as the objects change their location over time, requiring a continuous deployment of visual attention to avoid confusions between the objects¹⁸. 3D-MOT can be combined with fixation (still or tracking) while allocating the attention in the visual space to track other moving objects (covert attention) with the peripheral retina, a situation found in complex dynamic scene recognition^{18,19}. 3D-MOT stimulation programs displayed on monitors or TV screens have been shown to increase brain capacity for complex processes such as anticipation, eye-tracking, field of view and even decision-making in healthy and pathological participants²⁰⁻²². Recent work in low-vision patients with homonymous hemianopsia indicated a beneficial effect of audiovisual 3D-MOT IVR stimulation program using the Oculus Go on contrast sensitivity, fixation stability, reading speed and field of vision²³.

There are currently no visual rehabilitation strategies for children presenting visual field defects consecutive to a brain tumor or its treatment. The use of IVR in children aged 4-10 years old has not raised any safety concerns²⁴. Moreover, by using the remotely controlled and stand-alone Oculus Go, our strategy favors a home-based stimulation program which will increase compliance and adherence to the program.

2.3 RISK/BENEFIT ASSESSMENT

Potential Risks:

There are no risks for patients enrolled in the study. The use of IVR may cause moderate dizziness, nausea or disorientation for continuous stimulation above 10 minutes²⁵. If nausea, dizziness or disorientation is experienced during IVR stimulation, stopping the VR stimulation immediately restores normal condition²⁵. A recent study on the effects of IVR in 4-10 years old children indicate great tolerability with a prevalence of discomfort and induced effect of IVR lower than reported in adults²⁴.

Patients will be assessed for IVR sensitivity using the Virtual-Reality Induced Symptoms and Effects (VRISE) questionnaire score at inclusion²⁶ (exclusion criteria: three (3) consecutive VRISE score < 25).

At-home VR stimulation will be 5 minutes of continuous stimulation as specified in the “Study Intervention” section, below the critical 10 minutes threshold inducing effects and symptoms^{25,26}.

There are no risks for the community/public nor for the institution.

Potential Benefits:

We anticipate the HH patients will be able to adhere and comply to the home-based audiovisual stimulation program without any symptoms or effects.

We expect the potential benefits IVR stimulation will correspond to:

- an improved fixation stability,
- an enhanced reading speed.
- an improved field of vision

All together increasing self-dependency and quality of life which ultimately impact health care cost by:

- reducing the burden of disease,
- decrease of the global cost of vision impairment.

3 OBJECTIVES AND ENDPOINTS

No visual rehabilitation procedures are currently existing for children with visual field loss consecutive to brain tumor. The visual and auditory modalities of the 3D-MOT IVR stimulation program could potentially improve visual perception in the peripheral fields and saccades/volitional eye movements towards pre-designated targets. Improved oculomotor control will also result in better fixation stability which in turn ameliorates visual perception (reading, visual field).

PRIMARY OBJECTIVE:

Feasibility:

- Adherence to the home-based stimulation protocol. Each time the patients performed an audiovisual IVR session, data about the session (device ID#, subject #, date/time, time to complete the task/block, number of tasks/blocks performed, total stimulation time, total duration of the session) are recorded by the NeurofyResearch application in the Oculus Go and sent through Wi-Fi to a dedicated and secured laboratory computer.
- VRISE questionnaire scores recorded before and after each session and sent through Wi-Fi to a dedicated and secured laboratory computer in real-time.
- Retention rate.

SECONDARY OBJECTIVE:

Secondary endpoint measures will be performed at Toronto Western hospital during baseline and final visit (visit 1 and 6) and at 1 month (visit 7) and 6 months (visit 8) follow-up.

Visual acuity:

- Best Corrected Visual Acuity (BCVA) scores for distance and near vision – ETDRS/Colenbrander charts.
- Fixation stability - MAIA microperimeter, CentreVue

- Contrast sensitivity – FACT test.

Field of Vision:

- Humphrey full field 120 – Humphrey Field Analyzer 3, Zeiss
- Esterman binocular field - Humphrey Field Analyzer 3, Zeiss

Reading Speed:

- Minnesota Low Vision Reading - MNREAD test.

Quality of life:

- Children’s Vision Function Questionnaire (39 questions)

4 STUDY DESIGN

4.1 OVERALL DESIGN

We hypothesize that the home-based audiovisual 3D-MOT IVR stimulation program can be performed by HH pediatric patients and that this program will improve visual perception, reading speed and quality of life. For our trial design, we used the Pragmatic-Explanatory Continuum Indicator Summary (PRECIS-2) instrument, initiated and supported by the NIH Pragmatic Trials Collaborative Project to generalize knowledge about the conduct of pragmatic research. PRECIS-2 takes the innovative approach of translating ratings on nine domains related to trial design to a readily understood wheel format that communicates where the trial design falls on the explanatory (scored 1) - pragmatic (scored 5) continuum^{30,31} (Figure 1). All eligible patients in our study will be patients from care center at Sickkids, Toronto recruited through regular appointments made at the clinic (eligibility – recruitment). The setting of the trial corresponds to clinical visual care centers (setting). Information sheets will be given out to participants. Provider expertise corresponds to low-vision care center (organization). The group of patient will follow the study protocol from home, which can be usual practice in visual rehabilitation procedures. The delivery of the intervention is flexible with IVR stimulation every 2 days (± 1 day) at any time during the day (delivery). Adherence will be evaluated every 2 days; patients are free to “not-comply” and there will be no measures to improve adherence (adherence). Follow up of the primary outcome (adherence to the protocol) will be sent automatically through Wi-Fi to a dedicated and secured laboratory computer in real-time after each session. Secondary outcome will be assessed at the final visit after 4 weeks (follow-up secondary outcome at 1 month and 6 months). An Intention-to-treat will be performed for the analysis of the primary outcome (primary analysis). According to the PRECIS-2-wheel results (Figure 1), we propose an **interventional, pragmatic, single center pilot study** to assess **the feasibility and potential effectiveness of IVR stimulation in pediatric population of homonymous hemianopia patients**.

[figure not shown]

Figure 1: PRECIS-2 wheel indicating that our study is a pragmatic trial (scores >3).

Primary outcome corresponds to the feasibility of the study in terms of adherence, retention rates and recruitment. We specified, a priori, 4 feasibility objectives for our pilot study to be considered successful:

1. $\geq 8/10$ patient (80%) completed the protocol.
2. IVR stimulation protocol is considered complete if the patient performed ≥ 12 sessions out of 15.
3. ≤ 3 consecutive VRISE score < 25 per patient during the treatment period.
4. ≤ 2 dropouts (20%) for cybersickness (discomfort symptoms experienced in VR)

Completion of the sessions will be monitored in real-time. After each block, a data sheet (.csv, 2 kb) containing device ID#, subject #, date/time, time to complete the task/block, number of tasks/blocks performed, total stimulation time, total duration of the session will be sent though Wi-Fi to a dedicated and secured laboratory computer in real-time (if no Wi-Fi access is available at the end of each block, data are stored in the device and sent as soon as Wi-Fi is again available – data storage capacity 500 Mo. No extra costs are incurred to the patients' Wi-Fi plan for sending data). Each session contains 3 data sheets. A session is considered complete when 3 blocks of 5 min stimulation are performed. If no data sheets are received on the lab's computer for a period of 3 consecutive days or missed/incomplete sessions are observed, the participant's parent will be contacted by phone and email to identify the cause (no Wi-Fi, Oculus Go malfunction, dropout) and appropriate action will be taken. Before and after each session, the participant will answer to the VRISE questionnaire (5 questions scored 1 to 7 using the Oculus Go). After the completion of the questionnaire, the detailed score will be sent though Wi-Fi to a dedicated and secured laboratory computer in real-time.

Secondary outcome corresponds to potential effectiveness of IVR stimulation measured by visual perception and quality of life assessed following standard procedures used in low-vision rehabilitation²⁷ and collected at the low-vision clinic by ophthalmologists. Endpoints will measure change from baseline at 2 and 4 weeks in:

- Best Corrected Visual Acuity, distance and near vision (ETDRS chart, Colenbrander chart).
- Mean fixation stability (MAIA micro-perimeter).
- Contrast sensitivity (FACT test).
- Points not seen – Humphrey full field 120 (HFA3, Zeiss)
- Points not seen – Esterman binocular field (HFA3, Zeiss)
- Mean Reading speed (wpm – Minnesota Low Vision Reading test, MNREAD test²⁸).
- Quality of life scores (Children's Vision Function Questionnaire²⁹).

There will be no measure to minimize bias as this study is a feasibility study testing the adherence and compliance to the visual rehabilitation procedure.

INTERVENTION:

Immersive virtual-reality stimulation (IVR): 1 session of 3 blocks of 15 trials of 20 seconds each. Rest time is 1-2 minute(s) between blocks. 1 session lasts 19 minutes. 1 session every 2 days for 4 weeks (15 sessions total).

EXPECTED DURATION OF SUBJECT PARTICIPATION:

The duration of subject's participation is 7 months, including follow-up.

Treatment period: 4 weeks

Follow-up period: 6 months

EXPECTED FREQUENCY AND DURATION OF STUDY VISITS FOR STUDY PARTICIPANTS

Screening/inclusion visit: 1-1.5 hours

Baseline assessment visit: 1.5 hours (visit 1)

Intermediate assessment: 1.5 hours (visit 2)

Final assessment visit: 1.5 hours (visit 3)

Follow-up visit 1 month: 1.5 hours (visit 4)

Follow-up visit 6 months: 1.5 hours (visit 5)

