6 STUDY INTERVENTION

6.1 STUDY INTERVENTION(S) ADMINISTRATION

6.1.1 STUDY INTERVENTION DESCRIPTION

The device used is the commercially available virtual-reality, standalone, head mounted display Oculus Quest 2 (Facebook Technologies, Qualcomm, Xiaomi). There are currently 34 clinical trials registered on Clinicaltrials.gov using the Oculus Go or Quest: 12 in the US and 4 in Canada. [name] lab (co-

investigator) is currently running a clinical study using the Oculus Quest 2 in elderly patient with macular degeneration (NCT04685824, UHN REB approval 20-6143). The application uploaded in this device is the NeurofyResearch application, developed and owned jointly by UHN and Neuropowertrain (Research and Collaboration Agreement). It is a modified version of the Neurofy application, owned by Neuropowertrain, used for perceptual/cognitive training in professional athletes.

[figure not shown]

Figure 2: representation of the 3D-MOT stimulation procedure:

1. 8 spheres appear in the headset **2.** One sphere is cued (red) and returns to yellow after 5 seconds. **3.** All spheres start moving randomly for 20 seconds. **4.** After 20 seconds, the spheres stop moving. **5.** The patient must select using laser pointer (white) the ball corresponding to the cued one. **6.** The result is displayed corresponding to either a hit (correct selection) or a miss (wrong selection). Sequence returns to 1. for the next trial.

Audiovisual IVR stimulation procedure

This procedure corresponds to:

- 1 session every 2 days (± 1 day) for 4 weeks.
- 1 session = 3 blocks of 15 audiovisual stimulation tasks (2 min break between each block).
- 1 task = 20 seconds audiovisual IVR stimulation (3D-MOT + correlated sound).

The audiovisual stimulation task (the *NeurofyResearch* application) involves the 3D multiple-object-tracking (3D-MOT) paradigm composed of 8 high-contrast spheres which features are adapted to the visual ability of low-vision patients (luminosity = 100cd/m², size = 1.57° of visual angle). The spheres move for 20 seconds following random linear paths, bouncing on one another and on the walls of a virtual 3D cube when collisions occur. The overall span of the movement of the spheres covers 80° and 60° of horizontal and vertical visual angle respectively. The initial speed of the spheres is adjustable, from 3°/s. to 240°/s. and determined during the inclusion visit (figure 2).

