6.1.2 DOSING AND ADMINISTRATION

The patient, comfortably seated, is asked to track the moving cued target (1 sphere) among moving distractors (7 spheres) for 20 seconds. A spatial sound (50Hz, 25-65dBHL) is correlated to the movement of the cued target. After 20 seconds, the movement stops and the patient is asked to select, using a laser pointer, the cued sphere among the distractors (mark-all procedure). If the selection is correct (i.e. corresponding to the cued target) a positive feedback sound is provided and the speed of the spheres in the next trial is increased by 0.05log. If the selection is incorrect (i.e. corresponding to a distractor) a negative feedback sound is provided and the speed of the spheres in the next trial is decreased by 0.05log (adaptive simple up-down staircase). After each block of 5 minutes, the system sends data relative to the time spent performing the tasks (primary outcome) to our dedicated and secured laboratory computer through Wi-Fi and resets. This procedure takes approximately 1 minute and can be stopped by the patient for a longer break in between blocks if necessary (time of the break is recorded). After 3 blocks, the system

stops and goes on stand-by mode until the next session. The next session (to be performed 48 hours later) will be automatically uploaded in the device and will be initiated by the patient.

Audiovisual IVR stimulation, 1 session every 2 days for 4 weeks (15 sessions). 1 session = 3 x 5 minutes audiovisual stimulation.

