9 STATISTICAL CONSIDERATIONS

9.1 STATISTICAL HYPOTHESES

- Primary Endpoint(s):

Feasibility is considered when the following primary endpoints criteria are met:

1. $\geq 8/10$ patient (80%) completed the protocol.
2. IVR stimulation protocol is considered complete if the patient performed ≥ 12 sessions out of 15.
3. ≤ 3 consecutive VRISE score < 25 per patient during the treatment period.
4. ≤ 2 dropouts (20%) for cybersickness (discomfort symptoms experienced in VR)

- Secondary Endpoint(s):

Secondary endpoint measures will be performed at Toronto Western hospital during baseline (visit 1), after 2 weeks (visit 2), after treatment at 4 weeks (visit 3) and at 1-month (visit 4) and 6 months (visit 5) follow-up. Results will be compared to baseline.

Visual acuity:

- Best Corrected Visual Acuity (BCVA) scores for distance and near vision – ETDRS/Colenbrander charts.
- Fixation stability - MAIA microperimeter, CentreVue
- Contrast sensitivity – FACT test.

Field of Vision:

- Humphrey full field 120 – Humphrey Field Analyzer 3, Zeiss
- Esterman binocular field - Humphrey Field Analyzer 3, Zeiss

Reading Speed:

- Minnesota Low Vision Reading - MNREAD test.

Quality of life:

- Children's Vision Function Questionnaire (39 questions)

- Exploratory Endpoint(s):

None

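### The nominal 48-hour interval gives 14 sessions before the day-28 visit, but the primary completion rule counts out of 15

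*Combined protocol and SAP*

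**What the plan says.** Wherever the plan gives a session count, it gives 15: in the synopsis, sections 4.1, 6.1.2 and 9.1, and the primary-outcome text of section 9.4. The spacing is described in four places.

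- Section 4.1, under the intervention: "1 session every 2 days for 4 weeks (15 sessions total".
- Section 6.1.2 gives the same count ("Audiovisual IVR stimulation, 1 session every 2 days for 4 weeks (15 sessions") and adds: "The next session (to be performed 48 hours later) will be automatically uploaded in the device and will be initiated by the patient".
- Section 4.1, on delivery, and section 6.1.1 add a tolerance: "The delivery of the intervention is flexible with IVR stimulation every 2 days (± 1 day) at any time during the day (delivery" and "1 session every 2 days (± 1 day) for 4 weeks".
- The Schedule of Activities (section 1.3) marks stimulation on individual days.

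The completion rule is the same in sections 4.1, 9.1 and 9.4: "IVR stimulation protocol is considered complete if the patient performed ≥ 12 sessions out of 15". Feasibility then requires at least 8 of 10 patients to complete. Section 9.1 places the final assessment "after treatment at 4 weeks (visit 3"; the Schedule of Activities puts that visit on day 28.

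**The concern.** The count of 15 is the denominator of the rule that classifies each child as a completer, and the number of completers decides feasibility. The stated interval and the stated treatment length do not produce that count, and the calendar produces it only through three consecutive session days that the text does not explain. How many sessions a child is offered before the final visit, and so how many can be missed, depends on which section the site follows. Adherence is the main thing this pilot measures, so that number should be fixed before any data arrive.

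**Working it through.** **Inputs.** Interval: 48 hours (section 6.1.2). Treatment period: 4 weeks (section 4.1). First treatment day: day 1; final visit: day 28 (section 1.3). Tolerance: ±1 day (sections 4.1 and 6.1.1). Completion threshold: 12 sessions, with 15 as the denominator (sections 4.1, 9.1 and 9.4).

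**1. Trying to reproduce 15 from the interval.**
- By division: 28 days / 2 days = 14.
- From day 1: days 1, 3, 5, ..., 27, which is (27 − 1)/2 + 1 = 14 sessions. The 15th falls on day 1 + 14 × 2 = 29, one day after the final visit.
- From day 0: days 0, 2, ..., 26, again 14 before day 28. The 15th falls on day 28 itself, where the Schedule of Activities has no stimulation mark.

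The figure of 15 is not reproduced from either start.

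**2. Reading the calendar.** Lining up the Day and IVR rows of section 1.3, the marks under Treatment fall on days 1, 3, 5, 7, 9, 11, 13, 14, 15, 17, 19, 21, 23, 25 and 27. That is 15 marks, with gaps of 2, 2, 2, 2, 2, 2, 1, 1, 2, 2, 2, 2, 2, 2 days. Without day 14 (the visit 2 column), 14 marks remain, all two days apart. The symptom-questionnaire row has the same pattern, and the visit 2 assessments line up with day 14, so the extra mark does not look like a misread column.

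**3. The inclusion mark.** The IVR row also has a mark at inclusion on day 0, so 15 + 1 = 16 marks in all. The synopsis attaches the 15 to the home-based procedure, which suggests that the inclusion session is separate, but no section says so. The question bears on the denominator: the inclusion session plus the 14 odd-day sessions would also make 15, with day 14 then a 16th.

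**4. What ±1 day can do.** Fifteen sessions within days 1 to 27 need a mean gap of 26/14 = 1.86 days, so some gaps must be shorter than 48 hours.
- If the tolerance applies to gaps, the 1-day gaps around day 14 are allowed and 15 sessions fit.
- If it applies to dates on a strict two-day grid from day 1, the 15th nominal date (day 29) can move only to 29 − 1 = 28, the visit day.
- If it applies to the dates listed in the Schedule of Activities, 15 are already there.

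The plan does not say which is meant.

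**5. Effect on the rule.**

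| Sessions available | 12 as a share | Misses allowed |
|---|---|---|
| 15 | 12/15 = 80% | 15 − 12 = 3 |
| 14 | 12/14 = 85.7% | 14 − 12 = 2 |

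**The case against.** The best reply is that section 6.1.2 gives only a nominal interval. Delivery is described as flexible, and the ±1 day tolerance appears in section 6.1.1, immediately before the 48-hour sentence. Read together, gaps of 1 to 3 days are acceptable, the days 13-14-15 run lies within tolerance, and the Schedule of Activities lists 15 treatment dates. The endpoint also stays computable, because 12 sessions performed is a fixed count that can be reached with 14 or 15 on offer. All of this stands. It makes 15 possible, but it leaves the 48-hour sentence and the calendar in disagreement, the meaning of the tolerance unstated and the inclusion session unresolved.

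Three stronger readings are tempting, and the documents support none of them.

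- A reader might infer that the headset releases sessions on a 48-hour timer, so that a 15th cannot be done in time. Section 6.1.2 says that the next session is uploaded automatically and started by the patient. It gives no upload time and describes no lock.
- A reader might infer that 15 is simply wrong. The tolerance and the calendar together allow it.
- A reader might put a figure on the loss in the chance that at least 8 of 10 children complete. That needs an adherence rate, a within-child correlation, fixed session slots and no catch-up, none of which the plan states. The answer follows the assumptions. At 85% adherence without catch-up, 15 versus 14 sessions gives 0.74 versus 0.26 if sessions are independent, but 0.61 versus 0.52 at a within-child correlation of 0.5. At 95% adherence the difference is under 0.05 at every correlation tried (0 to 0.5), and with full catch-up it is nil. Section 4.1 says that missed sessions prompt a call to the parent and appropriate action, which does not exclude catch-up.

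**Conclusion.** The point holds as an inconsistency between the nominal interval and the session count. It does not show that the planned number is unattainable. At a steady 48 hours, 14 sessions fit before the day-28 visit, whether the first is on day 0 or day 1. The plan states 15, and its calendar shows 15 treatment marks only through two 1-day gaps, plus one inclusion mark of undefined status. The supportable effect is on the stringency of the completion rule: 80% with 3 misses allowed, or 85.7% with 2. The stricter figure assumes that the nominal interval is followed and that missed sessions are not made up; if all 15 can be done, the effect disappears. The arithmetic is certain, but which reading the site would follow is not. Severity is minor.

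**What to change.** Before enrolment, reconcile section 1.3, both statements in section 4.1 (delivery and intervention), section 6.1.1 and section 6.1.2 on three things: the interval between sessions, the session dates, and whether ±1 day applies to dates or to gaps. This review does not choose the schedule. Then make the denominator of the completion rule in sections 4.1, 9.1 and 9.4 equal the number of sessions that the reconciled schedule delivers by the final visit, and restate the rule if that number is not 15. State the first and last day on which a session counts, whether the inclusion session counts, and whether a missed session may be made up.

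The cost is wording only. The device already records the date and time of each session, so no patients, visits or data are added. Fixing the denominator now also prevents it from being chosen after adherence is known.
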